2.3.2 Secondary endpoints: Time to any progression and overall survival

3.0 PATIENT ELIGIBILITY

Subjects must meet all of the inclusion and exclusion criteria to be enrolled to the study. Study treatment may not begin until a subject is enrolled.

3.1 Inclusion Criteria

- 3.1.1 Patients with hepatocellular carcinoma are eligible for this trial. Hepatocellular carcinoma is defined as having at least one of the following:

- a. Biopsy proven hepatocellular carcinoma (HCC); or
- b. A discrete hepatic tumor(s) as defined by the Barcelona³⁵ criteria – for cirrhotic patients, >1cm with arterial hypervascularity and venous or delayed phase washout on CT or MRI [RECIST or mRECIST measurements will be captured for the study database and response assessment, however documentation of RECIST or mRECIST is not required at the time of enrollment.]

- 3.1.2 Patients must not have extrahepatic cancer.
- 3.1.3 Patients must not be eligible for curative liver resection or has refused resection.
- 3.1.4 Patients must have recovered from the acute effects of prior liver-directed therapy (e.g. RT, RFA, or TACE), and a minimum of 4 weeks must have passed since the last procedure and protocol therapy.

- 3.1.5 Patients must have a Zubrod performance status of ≤2.
- 3.1.6 Patients must have a life expectancy of at least 12 weeks.
- 3.1.7 Patients must be 18 years of age or older.
- 3.1.8 Patients must have adequate organ function as defined below.
 - Bone marrow: Platelets ≥30,000/mm³
 - Renal: BUN ≤40 mg/dl; creatinine ≤2.0 mg/dl
 - CPB score 8 and above for any size tumor
 - CPA-B7 score with tumors >3.5 cm
- 3.1.9 Patients must understand and be willing to sign an informed consent form approved for this purpose by the Institutional Review Board (IRB) of the University of Michigan Medical Center indicating that they are aware of the investigational aspects of the treatment and the potential risks.

3.2 Exclusion Criteria

- 3.2.1 Patients with known allergy to intravenous iodinated contrast agents
- 3.2.2 Patients with a contraindication to contrast-enhanced MRI

4.0 SUBJECT SCREENING AND REGISTRATION PROCEDURES

After informed consent is obtained and PRIOR to the initiation of protocol therapy all patients satisfying the inclusion/exclusion criteria will have eligibility confirmed by the Clinical Trials Office. The patient will not be considered registered and enrolled in the study until all information is confirmed by the Clinical Trials Office Data Manager.

5.0 TREATMENT PLAN

5.1 Treatment Dosage and Administration

Protocol treatment must start within 30 business days of enrollment to the study.

- 5.1.1 Global and regional assessment of liver function
 - 5.1.1.1 Global functional assessment with indocyanine green (ICG) clearance Preparation and administration of indocyanine green will be as per package insert by trained personnel in the Michigan Clinical Research Unit (MCRU). In some patients, indocyanine green will not be used, in favor of ALBI score.

5.1.1.1.1 Evaluations with ICG or ALBI will occur within 4 weeks prior to the start of RT, at approximately 4-6 weeks after the completion of the first 3/5 of planned treatments, and approximately 1-3 months after RT is completed.

5.1.1.1.2 For patients scheduled to have ICG testing for other reasons (including prior or subsequent enrollment in this or other protocols), every effort will be made to use results for both purposes, to avoid duplication, including extending windows by an extra 4 weeks in each direction.

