Although we developed the most accurate population-based model for predicting RILD for patients receiving fractionated radiation therapy, we are aware that there are limitations when applying this to individual patients, with variable sensitivity to radiation. Relying solely on the model unnecessarily exposes patients with high sensitivity to radiation to a high risk of toxicity, while at the same time, it also denies patients with average and low sensitivity to higher doses of radiotherapy, which could increase tumor control. In the preceding clinical trial, we individualized therapy based on the sensitivity of individual patient. Initial liver function was characterized by measuring the clearance of indocyanine green, a dye taken up by the plasma almost exclusively by the hepatic parenchymal cells and secreted entirely into the bile without undergoing any significant extrahepatic or enterohepatic circulation. It has been used extensively to predict mortality after liver resection and severe trauma^{27,28}. We delivered 3 treatments of SBRT, waited 4 weeks to detect subclinical decline in liver function, and adjusted radiation dose for 2 remaining treatments, based on the stability or decline in

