5.1.1.4 Functional assessment with MRI

MRIs will be obtained by trained personnel in the Department of Radiation Oncology at the University of Michigan.

5.1.1.4.1 Evaluations will occur within 4 weeks prior to the start of RT, at approximately 3-6 weeks after the completion of the first 3/5 of planned treatments, and approximately 1-3 months after RT is completed.

5.1.1.4.2 For patients scheduled to have MRI for other reasons (including prior or subsequent enrollment in this or other protocols), every effort will be made to use results for both purposes, to avoid duplication, including extending windows by an extra 4 weeks in each direction.

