5.1.2 Initial radiotherapy plan

5.1.2.1 CT with or without MRI simulation will be performed in treatment planning position, with appropriate immobilization, as is standard of care.

5.1.2.2 Radiation target volumes. The gross tumor volume (GTV) will be defined on CT or MRI. Appropriate patient-specific margins for motion will be added for patients unable to tolerate breath hold for treatment. No margin will be added for microscopic extent, as per routine clinical practice. A PTV margin will be added as per standard practice, typically 5mm radially and 8mm superiorly and inferiorly.

5.1.2.3 PTV Target Doses. Doses will be prescribed to a peripheral covering isodose covering the PTV, except in cases where this would exceed recommended doses to organs at risk (OARs). In these cases, heterogeneous dose distributions sparing these OARs are expected. The dose per fraction will be determined by the risk of liver damage, which will be fixed at $\leq 10\%$ for the initial 3/5 of treatment. The full treatment plan will be devised at this time in order to account for total normal tissue dose if patients are able to proceed with the entire treatment. The remaining 2/5 of treatment will be determined as per section 11 and potentially reduced based on liver function. Maximum prescribed tumor dose will be 55 Gy in 5 fractions, which we have shown that this dose is adequate for 95% local control at 2 years even for large tumors.

5.1.2.4 OAR Limits. Standard OAR limits in routine clinical practice will be applied and will take priority over target coverage.

5.1.3 Radiation Schedule. The first 3/5 of the treatment plan will be delivered in the initial phase. The dose of radiation will be based on baseline ICG or ALBI, CP score, and functional liver imaging for an NTCP < 10% for a predicted CP score change of greater than or equal to 2. After an approximately 4 week break and re-assessment of liver function with ICG testing or ALBI, the final 2/5 of treatment may be delivered, as per section 11. Patients who have, or would be predicted to have, unacceptable Toxicity (as defined in section 8.6) at the reassessment point will receive no additional therapy at that time.

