11.0 STATISTICAL CONSIDERATIONS

11.1 Study Design

This is a pilot study of individualized adaptive RT, which consists of 3/5 of a planned total course of treatment, a one month break, assessment of global and spatial liver function change using IC-Green or ALBI, and perfusion MRI, and the remainder of treatment adjusted for global and spatial changes in liver function. The primary endpoints are to establish the feasibility of this approach and to obtain preliminary estimates of safety and efficacy both overall and as they relate to treatment and patient characteristics. At the completion of this trial we will have the necessary data to define a SBRT treatment approach that is individualized and adaptive and ready to be compared to standard SBRT in a randomized trial.

Patients will have an initial plan with total dose chosen such that the estimated probability of toxicity (increase in CP of 2 points or more within 6 months of RT) from the first three of five planned treatments is at most 10%. In order to protect the safety of individual patients, after delivering 60% of the planned total treatment, there will be a 1 month break at the end of which, ALBI or ICG will be measured again and a new treatment plan will be developed.

This last course of treatment may be adapted (relative to the first course) globally in one of 2 ways. First, if there is no remaining enhancement on the MRI scan, no further radiation will be given because the tumor is likely to be cured. The second possible adaptation is intended

to prevent clinically significant decline in liver function in patients whose livers appear to be sensitive to RT. Child-Pugh (CP) score is a standard measure of liver function, and an increase of 2 points or more on this scale is considered clinically significant. Early changes in ICG retention and ALBI reveal subclinical changes in liver function that predict later liver toxicity, assessed by a change of 2 in CP score 6 months after treatment.

Maximizing tumor control and minimizing liver toxicity are competing objectives when selecting RT dose for these patients. To make this tradeoff explicit and quantitative, the dose during the second course of treatment will be selected as the minimum of

- 1) The dose that maximizes $\text{Prob}(\text{Local Control at 1 year}) - 4 * \text{P}(\text{Toxicity})$
- 2) The dose associated with a 25% estimated risk of toxicity.

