That is, additional dose is deemed to be beneficial if the increase in local control is at least 4 times greater than the increase in toxicity. The key advantage of this approach over an isotoxic approach is that patients are exposed to risk of toxicity in direct proportion to their benefit in terms of increased local control. Thus patients are not unnecessarily exposed to higher rates of toxicity (e.g. 20%) unless the improvement in expected local control is large enough. Similarly, patients are not constrained to an arbitrary rate of toxicity (e.g. 15 or 20%) if allowing the rate of toxicity to exceed this threshold results in a large enough increase in local control. At the same time we still place a hard upper limit of 25% on the risk of toxicity to any patient. The overall rate of toxicity in this population of patients is expected to be lower than 25%.

In the above, toxicity is defined as increase in CP of 2 points or more within 6 months of RT and local control is defined as absence of tumor progression within 1 year of treatment. For purposes of this dose selection, local control will be estimated from a simple Cox model as a function of tumor dose while the toxicity model will include the change in ICGR15 at the mid-treatment timepoint.

The decision to continue treating patients with further radiation is based on analysis of the information from the ICG results or ALBI, and not RECIST measurements. These measurements are recommended and are not required to determine patients' coming off-study treatment or study protocol. In addition, baseline measurements are not needed at the time of enrollment.

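### The 4-week extension for borrowed tests lets a mid-treatment ICG or perfusion MRI count from week 0, before the planned break ends, and for a prior-trial baseline ICG it conflicts with footnote 6's 30 days

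*Combined protocol and SAP*

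**What the plan says.** All references are to the combined protocol and SAP.

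- **Nominal windows.** Section 5.1.1.1.1 schedules ICG or ALBI "within 4 weeks prior to the start of RT, at approximately 4-6 weeks after the completion of the first 3/5 of planned treatments", and again about 1-3 months after RT. Section 5.1.1.3.1 gives the same windows for perfusion MRI. Section 5.1.1.4.1 differs at mid-treatment: functional MRI is due "at approximately 3-6 weeks after the completion of the first 3/5 of planned treatments".
- **Borrowed tests.** Sections 5.1.1.1.2 (ICG), 5.1.1.3.2 (perfusion MRI) and 5.1.1.4.2 (functional MRI) cover patients already due to have the test for another reason. To avoid duplication they ask staff to reuse the result, "including extending windows by an extra 4 weeks in each direction". None of the three says which of the time points this covers. The clause in 5.1.1.1.2 concerns ICG testing, not ALBI.
- **The break.** Section 5.1.3 gives the sequence as "After an approximately 4 week break and re-assessment of liver function with ICG testing or ALBI", with the final 2/5 to follow. Section 11.1 says "there will be a 1 month break at the end of which, ALBI or ICG will be measured again". Section 1.1.4 gives the reason for the interval in the preceding trial: the investigators "waited 4 weeks to detect subclinical decline in liver function".
- **Use of the result.** For selecting the second-course dose, section 11.1 states that "the toxicity model will include the change in ICGR15 at the mid-treatment timepoint".
- **Baseline ICG from a prior trial.** Footnote 6 to the table in section 6.4 accepts such a test as the pre-treatment assessment only if it was done no more than 30 days before the new RT course.

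**The concern.** The break lets a subclinical loss of liver function show itself before the rest of the dose is fixed. A test taken at the start of the break gives that loss no time to appear. If such a test were accepted, the change in ICGR15 might look smaller than it would at week 4, and the predicted toxicity might be too low for a patient whose liver is sensitive to radiation. Under section 11.1 that prediction enters both parts of the dose rule: the penalty of 4 times P(Toxicity), and the cap at the dose carrying a 25% estimated risk. An early MRI does not enter P(Toxicity), but section 5.1.4 uses it to reshape the dose distribution.

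Nothing else in the text restores a minimum interval. Sections 5.6.1 and 5.7 require a mid-treatment ICG (5.7 also accepts bloodwork for ALBI) but give no earliest date. Footnote 4 to the events table repeats the ICG only for a patient who does not at first qualify for the final phase, so a falsely reassuring early result would trigger no repeat.

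The baseline issue is separate. Two rules for the same borrowed ICG give different age limits, so staff cannot tell whether a test more than 30 days old may serve as the reference for the mid-treatment change.

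**Working it through.** The plan states no figure for the extended windows, so there is none to reproduce. The check is calendar arithmetic on the stated limits.

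**Inputs.** Mid-treatment window: 4-6 weeks for ICG (5.1.1.1.1) and perfusion MRI (5.1.1.3.1), 3-6 weeks for functional MRI (5.1.1.4.1). Baseline window: 4 weeks before RT. Extension: 4 weeks each way. Break: about 4 weeks (5.1.3). Footnote 6 limit: 30 days.

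**Step 1, mid-treatment.** Extended window = [lower limit − 4, upper limit + 4], in weeks after the first 3/5.

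| Test | Nominal | Extended | Usable | Time lost on the early side |
|---|---|---|---|---|
| ICG | 4 to 6 | 4 − 4 = 0 to 6 + 4 = 10 | 0 to 10 | 4 weeks |
| Perfusion MRI | 4 to 6 | 0 to 10 | 0 to 10 | 4 weeks |
| Functional MRI | 3 to 6 | 3 − 4 = −1 to 6 + 4 = 10 | 0 to 10 | 3 weeks |

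The functional MRI limit of −1 is cut to 0 because the window is counted from completion of the first 3/5. A literal limit that falls before that completion suggests the clause was not checked against this time point.

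**Step 2, comparison with the break.** Sections 5.1.3 and 11.1 put reassessment at about week 4. For ICG and perfusion MRI, the extended window therefore admits the whole break. These are calendar limits, not probabilities that a test falls there.

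**Step 3, baseline ICG from a prior trial.**

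- Limit under 5.1.1.1.2: (4 + 4) × 7 = 56 days before RT.
- Limit under footnote 6: 30 days before RT.
- Conflict: 56 − 30 = 26 days. A test at days 31-56 is allowed by one rule and barred by the other.
- Footnote 6 against the nominal window: 30 − 4 × 7 = 2 days of extra room.

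**What cannot be computed.** The documents give neither the number of patients who would borrow a mid-treatment test nor a time course of ICG change after RT. Neither the frequency nor the size of an understated risk can be estimated.

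**The case against.** **The route is narrow.** The clause's own examples are earlier and later enrollments, which bear mainly on baseline and post-RT tests. Concurrent enrollment is mentioned only in section 6.3, for follow-up. Under 5.6.4 a patient who joins a later liver radiation trial leaves the first enrollment. A borrowed mid-treatment test would have to come from the clause's general wording about other reasons. This stands, and it is why few patients are likely to be affected. It does not close the gap, because the general wording is unrestricted and the clause pushes staff toward reuse.

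**More specific text sets the timing.** Sections 5.1.3 and 11.1 and the column heading in 6.4 all place reassessment at 4 weeks or later. That shows the intent, but no sentence says these provisions override the extension. Likewise footnote 6 can be read as the special rule for a prior-trial ICG, but the protocol states no order of precedence.

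**Other checks protect the patient.** Bilirubin, INR and MELD/CTP are scheduled at 4-6 weeks. Section 5.2 holds RT for ALBI or Child-Pugh worsening. Section 5.1.3 bars more RT after actual or predicted unacceptable toxicity. Section 1.1.4 rates ALBI at least as useful as ICG, and 11.1 lets either inform the decision to continue. This protection is real but partial: ICG is used to show change before the clinical scores move, a predicted toxicity may rest on the same early ICG, and 11.1 names only ICGR15 as the mid-treatment input to the toxicity model.

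**Stronger readings the documents do not support.** A reader might infer that patients will be overdosed, or that an early ICG is known to be biased low. Section 1.1.4 says why the investigators waited, not how an earlier value would differ, so the understatement is plausible but not shown. A reader might also treat any functional MRI before the break ends as a defect. Its nominal window already opens at about 3 weeks, so only the loss of that limit comes from the extension. Nor does the 30-day conflict reach MRI, since footnote 6 covers ICG only.

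**Conclusion.** The point holds, at minor severity. Read literally, the extension admits a borrowed mid-treatment ICG or perfusion MRI from week 0 instead of about week 4, and a functional MRI from week 0 instead of about week 3. For ICG this defeats the waiting period behind the named mid-treatment input to the dose rule. Separately, the two age limits for a prior-trial baseline ICG differ by 26 days.

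The conclusion assumes that the plural wording in the three clauses covers all time points, and that no unstated rule of precedence applies. It concerns borrowed tests only. Patients whose global liver function is followed by ALBI are not affected by the ICG clause. No claim is made about how many patients are affected or how far their risk would be misjudged.

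**What to change.** 1. In 5.1.1.1.2, 5.1.1.3.2 and 5.1.1.4.2, add one sentence: the 4-week extension does not apply to the early side of the mid-treatment window. A borrowed test must fall no earlier than about 4 weeks after the first 3/5 for ICG and perfusion MRI, and no earlier than about 3 weeks for functional MRI.
2. In 5.1.1.1.2, apply footnote 6's 30-day limit to a borrowed baseline ICG, so that one limit governs.

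The late side at mid-treatment, the post-RT extension, the baseline MRI extension and the approximate wording of the windows can stay. No change to the planned analyses is needed.

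The cost is an occasional scheduled test in place of a borrowed one. At baseline, a borrowed ICG gains only 2 days over the nominal 28-day window, so borrowing there would become rarer.

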5.1.1.2 Baseline bloodwork and physical exam to obtain ALBI and Child Pugh score

5.1.1.3 Regional functional assessment with perfusion MRI

MRIs will be obtained by trained personnel in the Department of Radiation Oncology at the University of Michigan.

5.1.1.3.1 Evaluations will occur within 4 weeks prior to the start of RT, at approximately 4-6 weeks after the completion of the first 3/5 of planned treatments, and approximately 1-3 months after RT is completed.

5.1.1.3.2 For patients scheduled to have perfusion MRI for other reasons (including prior or subsequent enrollment in this or other protocols), every effort will be made to use results for both purposes, to avoid duplication, including extending windows by an extra 4 weeks in each direction.

5.1.1.4 Functional assessment with MRI

MRIs will be obtained by trained personnel in the Department of Radiation Oncology at the University of Michigan.

5.1.1.4.1 Evaluations will occur within 4 weeks prior to the start of RT, at approximately 3-6 weeks after the completion of the first 3/5 of planned treatments, and approximately 1-3 months after RT is completed.

5.1.1.4.2 For patients scheduled to have MRI for other reasons (including prior or subsequent enrollment in this or other protocols), every effort will be made to use results for both purposes, to avoid duplication, including extending windows by an extra 4 weeks in each direction.

5.1.2 Initial radiotherapy plan

5.1.2.1 CT with or without MRI simulation will be performed in treatment planning position, with appropriate immobilization, as is standard of care.

5.1.2.2 Radiation target volumes. The gross tumor volume (GTV) will be defined on CT or MRI. Appropriate patient-specific margins for motion will be added for patients unable to tolerate breath hold for treatment. No margin will be added for microscopic extent, as per routine clinical practice. A PTV margin will be added as per standard practice, typically 5mm radially and 8mm superiorly and inferiorly.

5.1.2.3 PTV Target Doses. Doses will be prescribed to a peripheral covering isodose covering the PTV, except in cases where this would exceed recommended doses to organs at risk (OARs). In these cases, heterogeneous dose distributions sparing these OARs are expected. The dose per fraction will be determined by the risk of liver damage, which will be fixed at $\leq 10\%$ for the initial 3/5 of treatment. The full treatment plan will be devised at this time in order to account for total normal tissue dose if patients are able to proceed with the entire treatment. The remaining 2/5 of treatment will be determined as per section 11 and potentially reduced based on liver function. Maximum prescribed tumor dose will be 55 Gy in 5 fractions, which we have shown that this dose is adequate for 95% local control at 2 years even for large tumors.

5.1.2.4 OAR Limits. Standard OAR limits in routine clinical practice will be applied and will take priority over target coverage.

5.1.3 Radiation Schedule. The first 3/5 of the treatment plan will be delivered in the initial phase. The dose of radiation will be based on baseline ICG or ALBI, CP score, and functional liver imaging for an NTCP < 10% for a predicted CP score change of greater than or equal to 2. After an approximately 4 week break and re-assessment of liver function with ICG testing or ALBI, the final 2/5 of treatment may be delivered, as per section 11. Patients who have, or would be predicted to have, unacceptable Toxicity (as defined in section 8.6) at the reassessment point will receive no additional therapy at that time.

5.1.4 Adaptive radiotherapy plan for the final 2/5 of treatment. Each patient will be treated in two parts. In the first part, the dose will be determined using the current normal tissue complication probability (NTCP) model and spatial liver function considered in treatment planning. The patient's baseline and 2nd global and spatial liver function assessments will be used to individualize the second part of treatment. Based on the MRI, adjustments in the dose distribution will be made to maximize remaining liver function and target active tumor subvolumes. Accumulated data from the trial will be used to update the individualization model.

